C.2. Study Overview. *Suubi4Stigma*, a mixed-methods sequential explanatory study,⁹³ will address the urgent need for theoretically and empirically informed interventions that seek to reduce HIV/AIDS-associated stigma and its negative impact on child health and psychosocial well-being. We will test the feasibility, acceptability and preliminary effects of the G-CBT versus MFG intervention, two evidence-based interventions that have, to date, been extensively used to address mental health functioning among children and adolescents. Specifically, clinics will be randomized to one of three study arms (see C.3). The conceptual model (Fig 1) specifies the expected relationship between the intervention arms, mechanisms and potential outcomes.

Figure 2. *Suubi4Stigma* Assessment

usual (n=3 clinics; 30 child-caregiver dyads); 2) G-CBT intervention + usual care (n=3 clinics; 30 child-caregiver dyads); and 3) MFG intervention + usual care (n=3 clinics; 30 child-caregiver dyads). Both treatment and control arms will be delivered over a 3-month period. Data will be collected at baseline (pre-intervention), 3-months and 6-months post-intervention initiation. Children in the same clinic will be assigned to the same study condition to avoid contamination (Fig.2).

C.3.1 Study Inclusion/Exclusion Criteria: *Inclusion criteria for children:* The target population for this study is CLWH enrolled in care at a health clinic that has partnered with ICHAD ([name] et al.; *Suubi+Adherence* study). Child inclusion criteria are: 1) HIV+ status- defined as a child tested with confirmation by medical report and has been disclosed to; 2) prescribed ART; 3) living within a family (defined broadly - not necessarily with biological parents); and 4) ages 10 to 14. All eligible CLWH from a particular household will be enrolled in the study and will be assigned to the same study condition. *Inclusion criteria for parents/caregiving families.* Caregivers of CLWH who agree to participate in the study. *Exclusion criteria* includes a significant cognitive impairment of the child or parent that interferes with understanding the informed consent process. *Inclusion criteria for clinics.* Clinics registered and supported by the government to provide ART to CLWH in Masaka.

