b) *Acceptability.* We will adapt satisfaction surveys, (e.g., the Client Satisfaction Questionnaire (CSQ-8)) to assess acceptability.¹⁶⁰ Items include: "How satisfied were you with the program?", "How helpful was the program in addressing HIV-associated stigma?" and "How likely are you to recommend this program to other families with CLHA?" Given the modest sample size, quantitative analyses of intervention data will be largely descriptive and concentrate on tabulating and summarizing satisfaction outcomes. In regards to hypotheses and methods for primary preliminary/exploratory analyses *to assess study feasibility*, we expect that: **H1:** Following intervention, relative to the control group, participants in both treatment arms (G-CBT and MFG) will have: **H1a:** lower mean count of children reporting HIV/AIDS-associated stigma; **H1b:** lower mean levels of reported HIV/AIDS-associated stigma and improved child psychosocial functioning; **H1c:** lower mean levels of reported child mental health challenges; **H1d:** higher mean levels of adherence. **H2:** Following intervention, relative to the CBT intervention arm, participants in the MFG intervention will have: **H2a:** lower mean count of children reporting HIV/AIDS-associated stigma; **H2b:** lower mean levels of reported HIV/AIDS-associated stigma and improved child psychosocial functioning; **H2c:** lower mean levels of reported child mental health challenges; **H2d:** higher mean levels of adherence. Children will be the unit of analysis for these primary preliminary analyses. We will plot means by group over time to describe overall patterns of change. We will use linear mixed models (LMMs) to evaluate the proposed hypotheses. We will fit LMMs to ensure that all requisite information is available to perform the types of analyses typically undertaken in a formal RCT of intervention efficacy and to obtain valuable effect size information. LMMs will include random intercepts for clinic membership and random intercepts and slopes for subjects (three-level models). Due to the modest sample size, significance testing will be de-emphasized. Similarly, although the modest sample size precludes formal investigation of moderation, we will use the same LMM approach described above to compare children across study arms over time on the moderators listed in Table 1. Additional analyses will consider the role of child gender as a moderator in line with NIH guidelines addressing the importance of sex and gender as critical moderators. These moderation analyses will be secondary exploratory analyses. Additional exploratory analyses will study parents and children jointly as the unit of analysis via dyadic analysis methods such as actor-partner and means-and-deviation models to quantify parent vs. child stigma effects and between- vs. within-dyad effects on mental health outcomes.^{161,162}

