
Power Analyses. Although the study purpose is to determine preliminary feasibility and acceptability, rather than conduct formal hypothesis tests, we conducted several power analyses using NCSS PASS to supply additional information. Our power analyses assume $\alpha=.05$, power=.80, 81 participants retained at the final time point following 10% estimated attrition, and a clinic-based conservative unconditional ICC of 9.3% based on our previous SUUBI study of mental health in Uganda children.¹⁶³ For the target enrollment proportion of 70% to assess feasibility, the width to the limit of the confidence interval is 27.9% (standardized distance: .32). For continuous standard normal variables to assess acceptability (e.g., CSQ-8), the distance from the mean to the confidence limit is .30. These distances to confidence limits are between small (.20) and medium (.50) effect sizes. For preliminary efficacy exploratory analyses with two time points and paired comparisons of two out of the three groups at 81/3=27 participants per group (N=54 per comparison), minimum detectable standardized mean differences for continuous outcomes ranged from .79 to .97 for within-subjects correlations r ranging from .20 to .80. In sum, our study is powered to detect small-medium distances to confidence limits for descriptive statistics and large longitudinal analysis effects, though hypothesis testing is not the study focus.

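### With the assumed clinic ICC, the detectable differences of .79 to .97 hold only on child-level degrees of freedom; on clinic-level df they are about .94 to 1.28, and the mixed model names no df method

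*Combined protocol and SAP*

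**What the plan says.** C.2 Study Overview makes the clinic the unit of randomisation: "clinics will be randomized to one of three study arms (see C.3". Each arm has three clinics and 30 dyads, assessed at baseline, 3 months and 6 months.

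C.3.6 Data Analysis, Aim 1, makes the child the unit of analysis and specifies "LMMs will include random intercepts for clinic membership and random intercepts and slopes for subjects (three-level models". It lists no fixed effects, target visit or df method. H1 is introduced by "Following intervention, relative to the control group, participants in both treatment arms (G-CBT and MFG) will have" and is worded mostly as mean levels. The same paragraph adds "We will plot means by group over time to describe overall patterns of change". The models are there "to perform the types of analyses typically undertaken in a formal RCT of intervention efficacy and to obtain valuable effect size information", while significance testing is to be played down.

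Power Analyses assumes two-sample comparisons described as "paired comparisons of two out of the three groups at 81/3=27 participants per group (N=54 per comparison", power .80, alpha .05 and "a clinic-based conservative unconditional ICC of 9.3% based on our previous SUUBI study of mental health in Uganda children". It reports that "minimum detectable standardized mean differences for continuous outcomes ranged from .79 to .97 for within-subjects correlations r ranging from .20 to .80". No df is stated there either.

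**The concern.** With three clinics per arm, an arm comparison carries only 4 between-clinic df (two arms) or 6 (three arms pooled), however many children are measured. If the detectable differences were computed as though 54 children supplied the df, they are too small, and a later trial planned from them would start from an optimistic picture of what this pilot can resolve. The same gap affects the mixed model, because software defaults range from a normal reference to Satterthwaite df.

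A second, conditional issue concerns the contrast. The only clinic-level term is an intercept that is constant over time. It carries clinic variance in a comparison of levels, but it drops out of an arm-by-time comparison. If such a comparison is reported, clinic differences in change have nowhere to go in the model.

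**Working it through.** **Inputs.** From Power Analyses: 27 children per arm, ICC .093, r from .20 to .80, power .80, alpha .05 (two-sided assumed). From C.2: three clinics per arm, hence 27/3 = 9 retained children per clinic.

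**1. Reproducing the plan's figure.**
- Design effect = 1 + (9 − 1) × .093 = 1.744.
- Variance of the arm difference in the mean of two time points = (2/27) × 1.744 × (1 + r)/2. This is .0775 at r = .20 (SE .278) and .1163 at r = .80 (SE .341).
- Detectable difference = λ × SE, where λ is the noncentrality giving 80% power. On 52 df λ = 2.855, so 2.855 × .278 = .79 and 2.855 × .341 = .97. Both match.

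Other constructions fail or conflict with the text:
- A change contrast uses 2(1 − r) in place of (1 + r)/2, so it falls as r rises. On 52 df it runs from .98 to .49 without the ICC and from 1.30 to .65 with it. The stated range rises with r.
- The averaged level on 4 df with no ICC also gives .79 to .97, but it drops the ICC that the paragraph says was assumed.

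**2. The same contrast and ICC on between-clinic df.**

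| df | λ | r = .20 | r = .80 | Power at .79 / .97 |
|---|---|---|---|---|
| 52 | 2.855 | .79 | .97 | about .80 |
| 6 (three arms pooled) | 3.367 | .94 | 1.15 | about .66 |
| 4 (two arms) | 3.761 | 1.05 | 1.28 | about .57 |

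**3. Level interval from the planned model.** In 200,000 simulated trials (one visit, nine clinics of nine children, ICC .093), a nominal 95% interval using the clinic intercept covers about 92% with a normal reference and 93% on 52 df. The difference in clinic means on 4 df covers 95%. In separate REML fits of the three-visit model with no clinic difference in change, Satterthwaite df gave 94–95%.

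**4. Change interval, if one is reported.** Let s be the clinic share of the variance of change. The documents do not give it, so 0 to .093 is assumed. A child-level interval understates the variance by a factor of 1 + 8s if clinics in both compared arms vary, or 1 + 4s if only one arm's clinics vary (a treated arm against control). Approximate coverage is 2Φ(1.96/√factor) − 1.

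| s | factor, one arm / both | coverage, one arm / both |
|---|---|---|
| 0 | 1 / 1 | 95% / 95% |
| .02 | 1.08 / 1.16 | 94% / 93% |
| .093 | 1.372 / 1.744 | 91% / 86% |

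Simulation on 52 df agrees (.941/.931 at .02; .905/.860 at .093). REML fits of the planned random effects with Satterthwaite df gave about one point less (.931/.921 and .902/.846). Satterthwaite does not help here, because the contrast contains no clinic variance term for it to act on.

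**5. Cost in width.** With s = 0, mean half-widths in SDs of change are .544 (52 df), .64 (6 df) and .71 (4 df). That is about 18% and 31% wider.

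**The case against.** The plan leans towards level. The hypotheses mostly compare mean levels after the intervention, and the detectable differences reproduce as a level contrast. For a level contrast the clinic intercept does its job, and what is missing is the df. That stands, and it is why the change issue is stated only conditionally. A reader might infer that the model ignores clustering, or that change is the planned contrast. The documents support neither. The plot of means over time and the child slopes are compatible with either contrast.

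The 52 df is inferred, since the plan states none. That also stands. But the only other match found needs the ICC to be dropped, so no reading tried delivers the stated range with both the stated ICC and clinic-level df.

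The study is a pilot. Testing is played down, no interval is promised for these contrasts, and feasibility and acceptability do not rest on this model. This limits the consequence but does not remove it: the models are meant to supply effect-size information of the kind a formal trial uses, and playing down p-values does not correct a standard error or a detectable difference.

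**Conclusion.** The concern holds in this limited form. The stated .79 to .97 is not delivered at 80% power once the plan's own ICC is combined with between-clinic df. The figures are then 1.05 to 1.28 (4 df) or .94 to 1.15 (6 df), with power of about .57 or .66 at the stated effects. This rests on the averaged-level reconstruction, equal clinic sizes of nine and a two-sided test. The plan's broad conclusion that only large longitudinal effects are detectable survives; the numbers do not.

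For the model, the df gap costs two to three points of coverage in a level interval. The change issue is real only if a change contrast is reported and clinics differ in change. A reader might take 86% as the expected coverage. It requires the level ICC to carry over in full to change and clinics in both compared arms to vary, and the documents support neither assumption. At a share of 0 there is no loss.

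Nor does it follow that a pairwise 4-df clinic-mean interval must be the main analysis. Pooled 6 df, or a mixed model with small-sample df, is also defensible. Severity is low to moderate.

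**What to change.** 1. In Power Analyses, restate the detectable differences on clinic-level df for the contrast that will be used. For the averaged level these are 1.05 to 1.28 (4 df) or .94 to 1.15 (6 df). If change is used, the present figures do not apply. On 4 df, change gives 1.29 / 1.02 / .65 SD at r = .2 / .5 / .8 with no clinic share, and 1.71 / 1.35 / .85 if a share of .093 is assumed in both arms.
2. In C.3.6 Data Analysis, Aim 1, state that arm contrasts use clinic-level small-sample df (Satterthwaite, Kenward-Roger or between-clinic df), and report a difference in clinic means alongside as a check.
3. If a change contrast is reported, base its interval on clinic mean changes with between-clinic df: 4 pairwise, or 6 pooled if all arms are taken to vary alike. Pooled coverage drops to 93–94% for MFG against G-CBT at shares of .05 to .093 if only treated clinics vary. Alternatively, add a clinic-level change effect to the mixed model, with the clinic-mean check alongside, because nine clinics estimate that variance poorly (zero in about 46%, 33% and 21% of trials at shares of .02, .05 and .093).

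The cost is some rewording, larger stated detectable differences, and change intervals about 18% (6 df) to 31% (4 df) wider if clinics do not in fact differ in change. No new data are required.

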Gender, family composition/structure, income, caregiver education & employment	Socio-demographic questionnaire <small>13-42, 100-137, 1-8</small>	n/a	B, 3, 6
Moderators			
Rural/urban/semi-urban: economic/household income, gender		n/a	B, 3, 6
Mechanisms of Change			
Shared experiences, peer and family support, family communication, interpersonal and coping skills	Semi-structured interviews	n/a	6
(Respondent: Adolescent)			
Mental Health Functioning	Youth Self-Report ¹³ Adapted Child Depression Inventory ¹⁵ Adapted Tennessee Self-Concept Scale (TSC-2) ¹ (tested in Suubi Studies)	n/a 0.65 0.81	B, 3, 6
Post-Traumatic Stress Disorder	Beck Hopelessness Scale ¹⁹ The Child PTSD Reaction Index ⁴⁰	0.79 0.88	B, 3, 6
Family Support	Social Support Behaviors Scale (SS-B) ⁴¹	0.77	B, 3, 6
Social Support	Friendship Qualities Scale ^{42,43}	0.81-0.88	B, 3, 6
Stigma and Shame	The Shame Questionnaire ^{44,45} Stigma-by-association scale for children ⁴⁶ HIV Stigma mechanism measure ⁴⁷	0.84- 0.89-0.90 0.87-0.89	B, 3, 6
Medication Adherence	Youth Self Report, ⁴⁸ Viral loads Pill Counting, Pharmacy Records	n/a n/a	B, 3, 6 Ongoing
Loneliness and Social Isolation	UCLA Loneliness Scale Version 3 ⁴⁹ The Lubben Social Network Scale (LSNS-18) ⁵⁰	0.89-0.94	B, 3, 6
Sexual risk taking	Adapted Youth AIDS Prevention Project used in CHAMP ⁵¹⁻⁵² Questions adapted from Auslander et al. ⁵³ & Stolni-Ngovo et al. ⁵²	n/a 0.72	
Intervention feedback	Semi-structured interviews	n/a	6
(Respondent: Caregiver)			
Stigma and Shame	AIDS-related stigma scale ⁵³ HIV/AIDS Stigma and Discrimination ⁵⁴	0.75 0.72-0.85	B, 3, 6
Family Relations	Family Environment Scale/Family Assessment Measure ^{55-56,58}	0.54-0.87	B, 3, 6
Intervention feedback	Semi-structured interviews	n/a	6
COST			
Cost of staff time, supplies, overhead for mental health and economic interventions	Project records, Admin. review	n/a	ongoing

conducted for all measures to ensure cultural validity. Process measures will be used to monitor fidelity and intervention implementation.

Intervention Delivery Fidelity. Independent observations using rating scales will be made with a random sample of 60% of intervention sessions for both G-CBT and MFG. These data will be used to assess: 1) the relationship between planned and actual implementation; 2) the integrity of implementation and; 3) how were altered to maximize effectiveness and acceptability.

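### The sentence specifying the moderation analysis compares the arms on the moderators themselves, so it shows balance, not effect modification; it needs an arm-by-moderator term on the outcome

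*Combined protocol and SAP*

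**What the plan says.** C.3.6 Data Analysis (Aim 1, in the text following the acceptability measures) sets out linear mixed models for H1 and H2, with a random intercept for clinic and a random intercept and slope for each child. It then concedes that the sample is too small for a formal study of moderation, and continues: "we will use the same LMM approach described above to compare children across study arms over time on the moderators listed in Table 1".

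Table 1 has a separate Moderators heading with the entry "Rural/urban/semi-urban: economic/household income, gender", collected at baseline, 3 and 6 months.

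The next sentence in C.3.6 plans further analyses of child gender in a moderator role, citing NIH guidelines, but gives no model. The paragraph then classifies the whole set: "These moderation analyses will be secondary exploratory analyses".

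Neither C.3.6 nor any other section writes an arm-by-moderator or arm-by-time-by-moderator term, or names the dependent variable of a moderation model. The Power Analyses paragraph covers only contrasts between arms.

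**The concern.** Moderation asks whether the arm effect on an outcome, such as stigma, differs between levels of a third variable. The null hypothesis is no arm-by-moderator interaction on that outcome. Comparing arms over time on the third variable answers something else: whether the arms have the same gender mix, income or location.

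- **Gender** is essentially fixed for a child over six months, so an arm-by-time effect on it is zero by construction.
- **Location** is fixed by the clinic (C.3.2 selects clinics by size and location), so the same applies.
- **Household income** can change, but the comparison then asks whether a stigma programme changes income.

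An analyst who followed the sentence could report chance imbalance between nine randomised clinics under the name of moderation. An analyst who guessed the intent would have to choose the outcome, the timing of the moderator and the form of the interaction after the data are in. C.3.6 says the models are fitted partly to obtain effect sizes for a later trial, and the literal analysis supplies none for moderators.

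**Working it through.** **Inputs from the documents.** Power Analyses: "81 participants retained at the final time point following 10% estimated attrition"; "paired comparisons of two out of the three groups at 81/3=27 participants per group (N=54 per comparison"; "a clinic-based conservative unconditional ICC of 9.3" per cent; α = .05 (two-sided assumed), power .80; within-child correlation r from .20 to .80. C.2: 3 clinics and 30 dyads per arm, so 10 per clinic, or 9 after 10% attrition.

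**Assumptions.** The documents give no gender split. An even split is used, with 30/70 as the other end of the range.

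**1. The plan's own figure.** The stated detectable differences are .79 to .97. They reproduce as a two-arm comparison of the mean of two visits:

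- Design effect = 1 + (9 − 1) × .093 = 1.744
- SE = √[(2/27) × 1.744 × (1 + r)/2] = .278 at r = .20 and .341 at r = .80
- Detectable difference (noncentral t, 52 df) ≈ 2.86 × SE = .795 and .973

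So the published figure concerns an arm contrast. It says nothing about moderation.

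**2. The same layout with an arm-by-gender interaction.** For a binary moderator with share p, the factor 1/[p(1 − p)] enters the variance; at p = .5 it is 4. If the clinic effect cancels within clinic, 1.744 is replaced by 1 − .093 = .907:

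- SE = √[(2/27) × 4 × .907 × (1 + r)/2] = .402 and .492
- Detectable difference in effect ≈ 2.86 × SE = 1.15 SD (r = .20) to 1.40 SD (r = .80)
- With the full design effect kept: 1.59 to 1.95 SD
- With a 30/70 split: 1.25 to 1.53 SD, or 1.74 to 2.13 SD with the full design effect

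**3. Does the literal comparison respond to moderation?** Simulation used 2 arms × 3 clinics × 9 children, ICC .093, r = .5, an even gender split, the mean of two visits and 4,000 runs per row.

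| True gender difference in effect (SD) | Arms compared on gender: rejects | Arm-by-gender interaction on outcome: rejects |
|---|---|---|
| 0 | 4.2% | 4.7% |
| 0.5 | 4.1% | 18% |
| 1 | 3.7% | 55% |
| 1.5 | 4.4% | 87% |
| 2 | 4.2% | 98% |
| 3 | 4.1% | 100% |

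The middle column stays flat, as it must: gender regressed on arm does not involve the outcome. The table shows which quantity is estimated; it is not a power comparison between two valid methods.

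**4. Range over the assumptions.** With a baseline-adjusted follow-up outcome and a 1 SD gender difference, the interaction rejects in 52% of runs at r = .5 and an even split. It rejects in 38% to 84% over r = .2 to .8 and a minority share of 30 to 50%. The literal comparison stays at about 4 to 5% throughout.

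**5. Precision of the corrected analysis.** For the baseline-adjusted outcome, SE ≈ √[(2/27)/(p(1 − p)) × .907 × (1 − r²)]:

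- r = .8, p = .5: √(.0741/.25 × .907 × .36) = .31; half-width 2.01 × .31 = .63 SD
- r = .2, p = .3: √(.0741/.21 × .907 × .96) = .55; half-width 2.01 × .55 = 1.12 SD

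Chance imbalance of gender within small clinics, and the parameters estimated, widen these slightly. Simulated half-widths are about 0.7 to 1.2 SD.

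**6. Location.** Nine clinics over three arms leave three per arm. If each arm had one rural, one semi-urban and one urban clinic (an assumption; the allocation is not stated), the nine arm-by-location cells would each hold one clinic. The interaction could then not be separated from the clinic intercept.

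**The case against.** The strongest reply is that nobody means to fit gender as a repeated outcome. The sentence follows a remark about moderation, refers back to models whose dependent variables are stigma, functioning, mental health and adherence, and is followed by a label calling these moderation analyses. This stands as a statement of intent: effect modification was evidently meant. It does not repair the text, which is the only model stated and names the moderators as what is compared.

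A reader might infer that the trial cannot detect moderation of any size, or that a programme working only in girls would leave no trace. The documents do not support that. A further analysis of gender in a moderator role is planned. Its model is unstated, but nothing there makes gender the dependent variable.

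A reader might also take the baseline, 3- and 6-month entry in Table 1 as proof that moderators are treated as outcomes. It is not: the Demographics row carries the same entry, so it is simply the questionnaire schedule.

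Two further points stand. The plan disclaims formal moderation inference and de-emphasises significance testing, so rejection rates matter less than the quantity estimated. And the figures above are for gender; no corresponding interaction power was computed for income or location. The small-sample caveat, however, excuses imprecision about the right quantity. It does not make a different quantity informative.

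**Conclusion.** The concern holds for one sentence. As worded, it yields arm balance on the moderators, or change over time in income, and no information on whether the treatment effect differs by moderator. That conclusion follows from the form of the comparison and does not depend on the simulation settings. The sizes quoted do: they assume r between .2 and .8, a minority gender share of 30 to 50%, and 27 retained children per arm in equal clinics.

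Severity is low. Only secondary exploratory results are touched, and the feasibility, acceptability, H1 and H2 analyses are unaffected. Even a correct interaction would detect only large differences, about 1.15 SD or more at 80% power in the plan's own layout with an even split.

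**What to change.** Replace the sentence with:

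> Exploratory moderation will be assessed by adding the baseline value of the moderator (child gender; household income) and its interaction with arm at each follow-up visit to the LMM for each outcome. Interaction estimates and arm effects by moderator level will be reported with 95% confidence intervals and no significance claims.

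State that the additional gender analysis uses this model. Describe the baseline distribution of the moderators by arm separately. Report location descriptively only, as arm means by location, and give the reason: it belongs to the clinic, and with nine clinics over three arms its interaction with arm may not be separable from the clinic intercept.

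The cost is a few sentences and the added moderator terms in each outcome model, with no new data or participants. The downside is wide intervals, about ±0.7 to 1.2 SD for a gender interaction between two arms.

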C.3.2. Research Setting: The child-caregiver dyads will be selected from 9 health clinics in the Masaka region where Reach the Youth-Uganda (RTY), our collaborating institution, collaborates with over 40 health clinics (see letters of support). Nine clinics will be randomly selected based on size (total number of CLWH served) and location (rural, semi-urban, urban).

C.3.3. Recruitment of Participants: *Screening and Recruitment.* Procedures tested in our previous studies (see C.1.) will be used. Participants will be identified and recruited from the healthcare clinics associated with RTY and ICHAD. A list of all eligible families will be created from medical records. Providers will present the project to adult caregivers of eligible children during appointments. If caregivers are interested, verbal consent to be contacted by research staff (on-site during clinics) will be requested (see human subjects sections).

Informed Consent. During the face-to-face meeting, the child's primary caregiver will read and sign a standard consent form. In doing so, the caregiver will be consenting to participation for themselves and their child. Children will sign an assent form that will be read aloud verbatim. If either the child or the caregiver refuses to participate, they will not be enrolled. (see human subjects section). *Enrollment.* Dyads will be enrolled in one of the three study arms. Only children and their caregivers who meet inclusion criteria will be selected (See C.3.1.). For each of the 9 clinics, a list of "eligible participants" will be generated and used to randomly select 10 children (and their caregivers), constituting the "actual" participants for that clinic. For the qualitative component, dyads with the highest, medium, and lowest levels of attendance in two treatment arms (6 clinics) will be identified post intervention. Two families within each of these groups in the 6 treatment clinics will be invited to participate in qualitative interviews (2x3x6=36 dyads). This sampling method will ensure that participants with varying experiences are represented. This will allow us to identify common patterns and

variations in participants' experiences. The sample size will be sufficient for theoretical saturation,⁹³⁻⁹⁶ and will allow for identification of common patterns and/or variations across participant experiences.

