Implementation/Evaluation. Having two facilitators per group will allow for detailed process notes on the implementation process and balancing “fidelity” and “fit” to local culture. Changes from the planned curriculum will be examined using process notes. Caregivers/children will report monthly on factors that affect their participation using an implementation checklist that assesses satisfaction and obstacles to program delivery: 1) factors interfering with youth or family participation (e.g. time, other priorities, stigma); 2) concrete obstacles (e.g. weather, transportation); and 3) site and staffing obstacles (e.g. time constraints).

C.3.6. Semi-structured Interviews (Aim 2). These interviews will: 1) Explore participants’ intervention experiences and perceived impact of the intervention on change mechanisms (including shared experiences, peer and family support, family communication, interpersonal and coping skills); and 2) Identify multi-level facilitators and barriers to G-CBT and MFG intervention, implementation and participation. Participants in the two treatment arms will be asked for feedback on intervention acceptability and relevance via semi-structured interviews upon intervention completion. Semi-structured in-depth interviews will be conducted with caregivers and CLWH separately at post intervention for each treatment arm. The interviews will provide rich data on participants’ processes and experiences with the program; processes behind key outcomes, mechanisms of change and mediating variables; and potential individual, family, contextual, programmatic, and structural factors affecting their experiences. At the end of the intervention, all facilitators will also be interviewed to gain a deeper understanding of implementation patterns and processes, including their views on sustainability. Interviews will be conducted in English or Luganda. Questions will be translated/back-translated by two team members fluent in both languages. Interviews will last about 1 hour and will be audio-taped.

C.3.6. Data Analysis

Aim 1: Feasibility and Acceptability. a) **Feasibility.** We will monitor recruitment rates and staff level of effort, number of screenings conducted, proportion eligible and agreed to enroll. Enrollment of 70% or higher will be

considered feasible.¹⁵⁹ We will also record the number of rescheduled, cancelled and missed sessions and assessments to inform estimation of staffing needs and retention protocols for a subsequent trial.

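### The 27.9% precision figure for 70% enrolment is the full width of the confidence interval, not the distance to a limit, and it is computed on children retained at the end of follow-up

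*Combined protocol and SAP*

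**What the plan says.** The Power Analyses paragraph sets common assumptions for all its figures: α of .05, "81 participants retained at the final time point following 10% estimated attrition", and a "conservative unconditional ICC of 9.3% based on our previous SUUBI study of mental health in Uganda children". For feasibility it then reports: "For the target enrollment proportion of 70% to assess feasibility, the width to the limit of the confidence interval is 27.9% (standardized distance: .32"). For acceptability it reports: "For continuous standard normal variables to assess acceptability (e.g., CSQ-8), the distance from the mean to the confidence limit is .30". It sums up both: "These distances to confidence limits are between small (.20) and medium (.50) effect sizes".

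Section C.3.6 (Data Analysis, Aim 1, Feasibility) describes what will be monitored, including "number of screenings conducted, proportion eligible and agreed to enroll", and treats enrolment of 70% or more as feasible. Section C.3.3 provides the starting point for such a proportion: "A list of all eligible families will be created from medical records". The number of families to be approached is not given.

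Under Acceptability, the survey items ask about the programme, for example "How helpful was the program in addressing HIV-associated stigma". That paragraph does not say who completes the survey. Section C.3.4 gives the control arm usual clinic care only.

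**The concern.** Two things do not fit. First, the wording presents 27.9% as a distance from the estimate to a confidence limit. Taken literally, that gives roughly 42.1% to 97.9% (70 − 27.9 and 70 + 27.9). An interval that wide would say almost nothing about a 70% threshold, and it is hard to square with a standardized distance of only .32. Second, children retained after attrition have all enrolled already. An enrolment proportion needs a denominator of families who were eligible and were asked.

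The same paragraph names feasibility and acceptability as the purpose of the study, and these are the only precision figures given for them. A reader who takes the label at face value carries away an interval about twice as wide as the one computed.

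**Working it through.** **Inputs.** From Power Analyses: 81 retained, ICC .093, α .05 (taken as two-sided; the plan does not say), target 70%. From C.3.3: 9 clinics with 10 children selected in each, so 90 enrolled. Retained per clinic: 81/9 = 9.

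**Reproducing the plan's figures.**

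1. Design effect = 1 + (9 − 1) × .093 = 1.744.
2. Effective n = 81/1.744 = 46.4, taken as 46. (Unrounded, the width in step 3 is 27.8 points; the printed 27.9 needs 46.)
3. Exact (Clopper-Pearson) 95% interval for .70 with n = 46: .547 to .826. Full width .826 − .547 = .279, the printed 27.9%.
4. Distances to the limits: .700 − .547 = .153 and .826 − .700 = .126.
5. Standardized lower distance (Cohen's h) = 2·arcsin√.70 − 2·arcsin√.547 = 1.982 − 1.665 = .317, the printed .32.
6. Half-width for a standard normal mean = t(.975, 45)/√46 = 2.014/6.782 = .297, the printed .30.

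One effective n returns all three figures. Of the three, only 27.9% is a full width.

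**Check that 27.9 points cannot be a distance.** A fall from .70 to .421 has h = .57, not .32, and would exceed the .50 bound the paragraph claims. As a simple Wald half-width, 27.9 points would need n = 1.96² × .21/.279² ≈ 10.4, against the 46 that the plan's inputs give.

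**Enrolment denominator.** The number approached is not given, so it is assumed here. To enrol 90 at 70% agreement, about 90/.70 ≈ 129 families must be approached, or 14.3 per clinic. At ICC .093 the design effect is 1 + 13.3 × .093 ≈ 2.24 and the effective n is 129/2.24 ≈ 57.6. The exact interval is .565 to .814: 13.5 points down, 11.4 up, full width 24.9. The ICC comes from a child mental-health study and is carried over to enrolment, so it too is varied (unrounded effective n, 9 clinics):

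| ICC | Full width, 81 retained | Full width, 129 approached | Full width, 150 approached |
|---|---|---|---|
| .05 | 24.8 | 21.4 | 20.5 |
| .093 | 27.8 | 24.9 | 24.1 |
| .15 | 31.3 | 28.9 | 28.3 |

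At each ICC the 81-child figure is the widest.

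**Acceptability.** The 81 include 81/3 = 27 controls, who receive no stigma programme. If only the other 54 children answer: effective n = 54/1.744 = 31.0, and the half-width is 2.042/√31.0 = .37 (t).

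**The case against.** The strongest reply is that this is a wording slip with no consequence. The paragraph offers these analyses as additional information, its conclusion rests on .32 and .30, and both reproduce. The .32 printed beside 27.9% already tells an attentive reader that the interval cannot run from 42% to 98%. The label understates precision and the 81-child basis is conservative, so nobody is led into overconfidence. All of that stands, and it is why the point is minor. It does not make the label right, and it does not make retained children an enrolment denominator.

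A reader might infer more in three directions:

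- **That the small-to-medium statement fails.** It does not. It rests on .32 and .30, and the .37 for programme children also lies between .20 and .50.
- **That the .30 is an error or has no stated basis.** The plan applies 81 participants and an ICC of 9.3% to all its figures, and .30 follows from them. What is missing is who answers the survey. Nothing says that controls will complete it, and nothing rules out caregivers. Figures for child-plus-caregiver respondents would need an assumption about correlation within dyads that the plan does not supply, so none is relied on here.
- **That precision is inadequate for each programme, or with so few clinics.** The plan sets no per-arm precision target. Its remark on satisfaction in each treatment arm concerns integration with the qualitative findings. Using degrees of freedom based on clinics would change the method as well as the respondents, so the result could not be compared with .30.

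**Conclusion.** The concern holds as a minor error of label and denominator. On the plan's own inputs, 27.9 points is the full width of the interval; the distances are 15.3 points down and 12.6 up. This rests on the design-effect and exact-interval reconstruction, which the plan does not spell out but which returns all three printed figures from one effective n.

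Using 81 retained children for an enrolment proportion is a mismatch with a modest effect: about 3 points of full width (27.9 against 24.9) if some 129 families are approached and the ICC of .093 applies. Both are assumptions. The direction was the same at every ICC tried from .05 to .15.

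For acceptability, the gap is the unnamed respondents. The move from .30 to about .37 applies only if the 54 programme children alone respond.

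**What to change.** In Power Analyses:

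- Call 27.9% the full width of the 95% interval, or replace it with 15.3 points below and 12.6 above 70%. Keep .32, described as the standardized distance to the lower limit.
- Compute enrolment precision on eligible families approached. State the number as an assumption (about 129 gives a full width of about 24.9 points) and say that the ICC of .093 is carried over from a mental-health outcome.

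In Acceptability, state who completes the satisfaction survey and in which arms. If it is children in the two programme arms only, restate .30 as about .37; the small-to-medium sentence can remain.

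The cost is a few sentences of text. No new data are needed.
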